5. INVESTIGATIONAL PLAN

5.1 Summary of Study Design

This is a randomized, double-blind, parallel-group, placebo-controlled, multicenter Phase III study that will evaluate the efficacy and safety of OKZ in subjects with moderately to severely active RA inadequately controlled by MTX therapy.

Inadequate response to MTX therapy is defined as a subject with at least 12 weeks of exposure prior to Screening and with either:

- Absence of any documented clinically significant response; or
- Documented initial clinical response with subsequent loss of that response or partial response

[figure not shown]
This study will be conducted at approximately 50 sites across 4 countries globally, which may include Russia, Belarus, Turkey, and Bulgaria. A total of 420 subjects will be randomized.

Subjects will be assessed for eligibility to enter the study during a 4-week Screening Period. Eligible subjects will be randomized at Visit 2 in a 1:1:1 ratio to 1 of 2 dosing frequencies (q2w or q4w) of 64 mg OKZ or to placebo as described in Section 5.2. The study will consist of a 24-week double-blind Treatment Period with the last dose of study treatment (OKZ or placebo) administered at Week 22 in all groups. After completion of the double-blind Treatment Period, subjects will be offered the opportunity to enter the long-term OLE study. Subjects who do not consent to participate in the OLE study will come to the End of Treatment (EoT) Visit (Visit 15, Week 24) 2 weeks after the last dose of the study treatment for scheduled assessments. After the EoT Visit, these subjects will be scheduled for Safety Follow-Up Visit SFU-1 (Week 26), Visit SFU-2 (Week 30), and Visit SFU-3 (Week 44) to perform adequate safety assessments. For subjects not entering the OLE, the total amount of time to complete the study will be approximately 48 weeks (inclusive of the Screening, Treatment, and Safety Follow-Up Periods).

Subjects who discontinue randomized study treatment early will adhere to the double-blind Treatment Period visit schedule outlined in Table 1 or Table 2 (as applicable), as if they were still receiving study treatment. In addition, all subjects who discontinue study treatment early will be required to attend the EoT Visit +2 weeks after the last dose of the study treatment, as well as Safety Follow-Up assessments +4, +8, and +22 weeks after the last dose of study treatment.

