A schematic of the study design is presented in Figure 1. The Schedule of Events to be conducted during the initial 24-week double-blind Treatment Period (Screening through Week 24) and the Safety Follow-Up Period (Week 24 through Week 44) is presented in Table 1 for all subjects who are not part of the sample-rich PK subpopulation. For subjects who have consented in a separate, optional ICF to be included in the sample-rich PK subpopulation, the Schedule of Events is presented in Table 2.

Figure 1 CL04041022 (CREDO 1) Study Schematic

Abbreviations: DMARD = disease-modifying anti-rheumatic drug; MTX = methotrexate; N = total number of subjects; n = number of subjects per treatment group; OKZ = olokizumab; OLE = open-label extension; q2w = once every 2 weeks; q4w = once every 4 weeks; R = randomization; RA = rheumatoid arthritis; SC = subcutaneous.

- After completion of the 24-week double-blind Treatment Period, subjects will either roll over into the long-term OLE study or return for Safety Follow-Up Visits at Weeks 26, 30, and 44 in the current study.
- At Week 14, subjects are classified as nonresponders if they do not improve by at least 20% in both swollen and tender joint counts (66-68 joint assessment).
- Starting at or as close as possible to Week 14, subjects classified as nonresponders are prescribed 1 or both of the 2 allowed DMARDs in addition to the study treatment, background MTX, and concomitant folic acid or equivalent.

Table 1 CL04041022 (CREDO 1) Schedule of Events (Double-Blind Treatment Period and Safety Follow-Up Period)

Assessments ^a	Randomized Double-Blind Treatment Period															Safety Follow-Up Period		
	1	2	3	4	5	6	7	8	9	10	11	12	13	14	15/EoT	SFU-1	SFU-2	SFU-3
Week	Screening	0/Baseline	1	2	4	6	8	10	12	14	16	18	20	22	24 (+2 ^b)	26 (+4 ^b)	30 (+8 ^b)	44 (+22 ^b)
Visit Window (days) for all subjects other than those included in the sample-rich PK subpopulation																		
	-28 to -1	±0	±2	±3	±3	±3	±3	±3	±3	±3	±3	±3	±3	±3	±3	±7	±7	±7
Obtain informed consent, optional PK informed consent, optional PG informed consent	✓ ^c																	
Subject number assigned via IWRS	✓																	
Determine eligibility	✓	✓																
Demography	✓																	
Medical history and current medical conditions	✓																	
Height	✓																	
Weight	✓	✓			✓		✓		✓			✓			✓	✓	✓	✓
Physical examination	✓ ^d	✓ ^d	✓	✓	✓	✓	✓	✓	✓ ^d	✓	✓	✓	✓	✓	✓ ^d	✓	✓	✓ ^d
Vital signs ^e	✓	✓ ^f	✓	✓	✓	✓	✓	✓	✓	✓	✓	✓	✓	✓	✓	✓	✓	✓

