6.14 Medical Treatment for Subjects after End of Study

After completion of the 24-week double-blind Treatment Period, subjects will either roll over into the long-term OLE study or enter the Safety Follow-Up Period. For subjects who complete the study without entering the OLE and for all subjects who discontinue study treatment prematurely, it is the responsibility of the Investigator to choose adequate treatment.

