7.6.1 Adverse Events

For the purposes of this study, an AE will be defined as any untoward medical occurrence in a subject or clinical investigation subject administered a pharmaceutical product and which does not necessarily have a causal relationship with this treatment. An AE can therefore be any of the following:

- Any unfavorable and unintended sign, symptom, or disease temporally associated with the use of a medicinal product, whether or not considered related to the medicinal product.
 - If the Investigator determines a laboratory abnormality to be clinically significant, it is considered a laboratory AE; however, if the abnormal laboratory value is consistent with a current diagnosis (or signs or symptoms if a diagnosis is not possible) and is not a clinically significant worsening from the baseline laboratory parameter, it should be documented accordingly without being reported as a separate laboratory AE.
- Any new disease or exacerbation of an existing disease (a worsening in the character, frequency, or severity of a known condition).

The Investigator is responsible for recording all AEs observed during the study from the time the subject signs the ICF. All AEs are recorded throughout the study until the last visit of the subject. The Investigator is responsible for the appropriate medical care of the subjects during the entire study.

Each AE is to be evaluated for duration, severity, seriousness, and causal relationship to the investigational drug. For all AEs, the Investigator must pursue and obtain information adequate both to determine the outcome of the AE and to assess whether it meets the criteria for classification as an SAE. The Investigator is required to assess causality as described below. For AEs with a causal relationship to the study treatment, follow-up by the Investigator is required until the event has resolved, it has a stable sequelae, the Investigator determines that it is no longer clinically significant, or the subject is lost to follow-up.

Severity

The severity of AEs will be characterized according to the CTCAE grades and definitions summarized in Table 6.

Table 6 CTCAE Grades and Corresponding AE Severity

CTCAE Grade	Corresponding AE Severity
Grade 1	Mild; asymptomatic or mild symptoms; clinical or diagnostic observations only; intervention not indicated
Grade 2	Moderate; minimal, local, or noninvasive intervention indicated; limiting age-appropriate instrumental ADL

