9.4.15 Safety Analyses

Analysis of safety endpoints (see Section 4.7) will be done based on the safety population. Subjects in the safety population will be analyzed according to the treatment they actually received. Additionally to the primary safety analysis, the incidence of AEs will be analyzed separately for subjects administered additional DMARDs as rescue medication during the period of treatment without rescue medication and with rescue medication.

Major components for the safety analysis will include:

- AEs will be solicited at every study visit, recorded, and coded according to the most recent version of the MedDRA.
- SAEs.
- Vital signs and physical examination findings.
- Laboratory parameters.
- ECG and other specialized tests findings.

All safety assessments will be summarized in a descriptive manner. Further details will be provided in the SAP.

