9.4.15.1 Adverse Events

All AEs will be analyzed in terms of descriptive statistics and qualitative analysis. Adverse events will be listed for each subject and summarized by SOC and PT according to the most recent version of the MedDRA. In addition, summaries of AEs by severity (evaluated using the CTCAE version 4.0) and relationship to study treatment will be presented. All safety and tolerability data recorded during the study will be listed and summarized by treatment group, and over time, as appropriate. Additionally to primary safety analysis, the incidence of AEs

will be analyzed separately for subjects administered additional DMARD as rescue medication during the period of treatment without rescue medication and with rescue medication.

Treatment-emergent AEs are defined as AEs that first occurred or worsened in severity after the first administration of the study treatment. Adverse event summaries will include incidence of TEAEs, SAEs including deaths, AEs that led to study treatment discontinuation, and AEs by maximum severity and relationship to study treatment. All summaries will be presented by MedDRA SOC and PT for each treatment group.

Safety/tolerability and AE data will be presented in individual listings.

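### Treatment-emergent AEs have a start but no common end, so crude incidences pool observation periods of 24 to 44 weeks that depend on whether a subject enters the open-label extension

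*Combined protocol and SAP*

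**What the plan says.** Section 9.4.15.1 gives the definition: "Treatment-emergent AEs are defined as AEs that first occurred or worsened in severity after the first administration of the study treatment". The planned output is stated as "Adverse event summaries will include incidence of TEAEs, SAEs including deaths, AEs that led to study treatment discontinuation", with further tables by severity and relationship, all by treatment group. Section 9.4.15 adds "All safety assessments will be summarized in a descriptive manner" and leaves further detail to the SAP.

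The observation period is set elsewhere:

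- Section 7.6.1: "All AEs are recorded throughout the study until the last visit of the subject".
- Section 5.1: "the last dose of study treatment (OKZ or placebo) administered at Week 22 in all groups". After the Treatment Period, "subjects will either roll over into the long-term OLE study or return for Safety Follow-Up Visits at Weeks 26, 30, and 44". Section 6.14 says the same.
- Section 7.6.5.4 puts the outer limit of AE collection at 22 weeks after the last dose.
- Section 5.2.2 explains that limit as about five half-lives of roughly 31 days.
- Sections 5.1 and 5.2 keep early discontinuers on the visit schedule to Week 24, with safety visits up to 22 weeks after their last dose.

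The only AE split by period in Sections 9.4.15 and 9.4.15.1 is before versus after rescue medication, in rescued subjects. Section 9.4.5 calculates duration of exposure but does not use it as an AE denominator. Sections 9.3 and 9.4.15 assign subjects to the treatment they actually received.

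**The concern.** A crude incidence compares arms fairly when both are observed for similar lengths of time. Here the length depends on a decision made at Week 24, after randomization. A completer who declines the OLE can contribute AEs for 20 weeks longer than one who accepts. If acceptance differs by arm, because of response, tolerability or the wish of placebo subjects for active drug, the arm with fewer OLE entrants shows a higher percentage even when the weekly risk is identical. If acceptance is equal, the arms remain comparable, but the percentage still refers to no defined period.

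Safety and tolerability are a stated secondary objective (Section 3.2), and the events of special interest in Section 7.6.3 include uncommon ones such as gastrointestinal perforation and malignancy. In relative terms the distortion is largest for uncommon events. Section 9.4.9.2 anticipates unequal dropout by arm for efficacy and adds a sensitivity analysis; the safety sections have no counterpart. Section 9.4.1 will report OLE enrolment by arm, so an imbalance would be visible, but no planned AE table would account for it.

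**Working it through.** **1. The plan's own follow-up figure.** Five half-lives of 31 days: 5 × 31 / 7 = 22.1 weeks, stated as 22. Last dose at Week 22 plus 22 weeks = Week 44. Screening 4 + treatment 24 + follow-up 20 = 48 weeks, as Section 5.1 states. The figures reproduce.

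**2. Length of AE observation by route.**

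- OLE entrant: to about Week 24.
- Completer not entering the OLE: to Week 44, and 44 / 24 = 1.83 times as long.
- Early discontinuer who stays in the study, last dose at week *t*: to the later of Week 24 and *t* + 22. This gives Week 24 for *t* = 0 or 2, Week 28 for 6, Week 34 for 12 and Week 40 for 18.

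Subjects who withdraw from the study may be observed for less than 24 weeks.

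**3. Effect on the crude incidence when there is no drug effect.** The documents give neither an AE hazard nor OLE entry by arm, so both are assumptions. Take a constant hazard, equal in all arms, and consider completers only. Let I24 be the 24-week incidence and *r* the share entering the OLE:

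- I44 = 1 − (1 − I24)^(44/24)
- crude incidence = *r* × I24 + (1 − *r*) × I44

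Worked example, I24 = 10%: I44 = 1 − 0.9^1.833 = 17.57%. With *r* = 95%: 0.95 × 10 + 0.05 × 17.57 = 10.38%. With *r* = 75%: 0.75 × 10 + 0.25 × 17.57 = 11.89%. The ratio is 1.146 one way and 0.873 the other.

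| I24 (assumed) | I44 | Crude, 95% enter OLE | Crude, 75% enter OLE | Difference (points) | Ratio, OKZ to placebo, if OKZ has 75% and placebo 95% | Same, shares reversed |
|---|---|---|---|---|---|---|
| 5% | 9.0% | 5.2% | 6.0% | 0.8 | 1.153 | 0.867 |
| 10% | 17.6% | 10.4% | 11.9% | 1.5 | 1.146 | 0.873 |
| 30% | 48.0% | 30.9% | 34.5% | 3.6 | 1.116 | 0.896 |
| 60% | 81.4% | 61.1% | 65.3% | 4.3 | 1.070 | 0.935 |

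Mean observation is 25 weeks at 95% entry (0.95 × 24 + 0.05 × 44) and 29 weeks at 75%.

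**4. Range.** With a 10-point gap (95% versus 85%) the ratios run from 1.035 to 1.076; with a 30-point gap (90% versus 60%), from 1.103 to 1.221. With equal entry the ratio is 1.000 at every incidence.

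**5. After the fix.** Over a fixed window to Week 24, every completer contributes 24 weeks, so under the same assumptions the ratio is 1.00 whatever the entry shares. A person-time rate over the whole period also returns 1.00, but only while the hazard stays constant after dosing stops. That is why the fixed window should carry the main comparison.

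**The case against.** The other side has several good points.

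- **Follow-up events belong in the safety record.** The 22-week follow-up exists because drug persists after the last dose. A reader might infer that events after Week 24 are contamination and should be dropped. Section 5.2.2 does not support that, and treating them as treatment-emergent is defensible. What stands is that they are not separated or put on a time base.
- **The window is not unlimited.** A reader might infer that events accrue indefinitely. Sections 7.6.1 and 7.6.5.4 end collection at the last visit, at most 22 weeks after the last dose. The gap is that the end differs between subjects.
- **The direction is unknown.** A reader might infer that OKZ incidences will be understated because responders stay on. Sections 5.1 and 5.2 offer the OLE to subjects completing treatment with no response criterion stated, and placebo subjects may be keener to obtain active drug. The only entry figures are from the earlier extensions in Section 2.2.3.1: 190 of 221 (86%) and 103 of 119 (87%), not split by arm.
- **Other treatment in follow-up.** Section 6.14 says that "it is the responsibility of the Investigator to choose adequate treatment", and a reader might infer that AEs of later therapy are charged to the randomized arm. Safety is analysed by treatment received. That sentence sits under care after the end of study, and Table 4 prohibits biologic DMARDs throughout the study. The point is stronger for early discontinuers, who may receive standard of care while attending visits (Section 9.4.9.2), but a Week 24 cut-off does not remove those events. The conclusion does not rest on it.
- **The model is simple.** A hazard that falls after dosing stops would shrink the effect, and early discontinuers soften the contrast between 24 and 44 weeks.
- **Safety is descriptive and detail is deferred.** No hypothesis test is affected, and Section 9.4.15.1 allows summaries over time where appropriate. But that wording commits to no period, and no SAP text in the document under review sets one.

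**Conclusion.** The point holds as a cheap improvement, not as a demonstrated error in the trial's conclusions. Followed as written, Section 9.4.15.1 yields one percentage per group over observation periods running from Week 24 to Week 44, fixed by a choice made after randomization. Between arms this matters only if OLE entry or early discontinuation differs. For a 20-point difference in entry, with assumed entry shares and a constant, equal hazard, the spurious ratio lies between about 0.87 and 1.15; for differences of 10 to 30 points, a ratio above 1 would be inflated by about 4% to 22%. The documents support neither a direction nor a particular size, and equal entry gives no between-arm bias.

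**What to change.** In Section 9.4.15.1 and the SAP:

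1. Make the main between-group TEAE tables cover first dose to a fixed Week 24 for all subjects in the safety population, by treatment received and regardless of treatment discontinuation. Do not offer the End of Treatment visit as an alternative cut-off. For early discontinuers it falls 2 weeks after the last dose, so the window would again depend on a post-randomization event, one plausibly related to toxicity.
2. Tabulate Safety Follow-Up events separately.
3. Add exposure-adjusted rates, as events per 100 patient-years of observation, for the whole period to 22 weeks after the last dose or OLE entry. Events that occur while drug persists are then still reported against time observed.

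The cost is SAP wording and a few extra tables from data already collected. No visit, procedure or clinical rule changes. It should be settled before unblinding, when Section 9.4 requires the SAP to be final.

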9.5 Subgroup Analysis

All subgroup analyses will be exploratory (post hoc) in nature. The details of these analyses will be described in the SAP and provided prior to the database lock. No specific subgroup analysis will be described in details in the protocol.

9.6 Safety Monitoring Committees

A DSMB and CVAC will oversee the study from a safety and CV monitoring perspective, as described in Section 7.6.4.

9.7 Interim Analyses

No interim analyses are planned for the study.

10. ETHICS

10.1 Institutional Review Board/Independent Ethics Committee

An IRB/IEC should approve the final protocol, including the final version of the ICF and any other written information and/or materials to be provided to the subjects. The Investigator will provide R-Pharm or R-Pharm's designee with documentation of IRB/IEC approval of the protocol and the ICFs before the study may begin at the study site(s). The Investigator should submit the written approval to R-Pharm or its designee before enrolment of any subject into the study.

R-Pharm or its designee should approve any modifications to the ICF that are needed to meet local requirements.

The Investigator will supply documentation to R-Pharm or R-Pharm's designee of required IRB/IEC's annual renewal of the protocol, and any approvals of revisions to the ICF or amendments to the protocol.

The Investigator will report promptly to the IRB/IEC, any new information that may adversely affect the safety of subjects or the conduct of the study. Similarly, the Investigator will submit written summaries of the study status to the IRB/IEC annually, or more frequently if requested by the IRB/IEC. Upon completion of the study, the Investigator will provide the ethics committee with a brief report of the outcome of the study, if required.

R-Pharm or its designee will handle the distribution of any of these documents to the national regulatory authorities.

R-Pharm or its designee will provide Regulatory Authorities, IRBs/IECs, and Investigators with safety updates/reports according to local requirements, including SUSARs, where relevant.

Each Investigator is responsible for providing the IRB/IEC with reports of any serious and unexpected adverse drug reactions from any other study conducted with the study treatment. R-Pharm or its designee will provide this information to the Investigator so that he/she can meet these reporting requirements.

10.2 Ethical Conduct of the Study

The GCP is an international ethical and scientific quality standard for designing, conducting, recording and reporting studies that involve the participation of human subjects. The study will be conducted in compliance with GCP and the applicable national regulations so as to

assure that the rights, safety and well-being of the participating study subjects are protected consistent with the ethical principles that have their origin in the Declaration of Helsinki.

10.3 Subject Information and Informed Consent

The ICFs (i.e., for the main study subjects, PK subpopulation, and for PG) will be used to explain the risks and benefits of study participation to the subject in simple terms before the subject will be entered into the study. The ICF(s) contain a statement that the consent is freely given, that the subject is aware of the risks and benefits of entering the study, and that the subject is free to withdraw from the study at any time. Written consent must be given by the subject and/or legal representative, after the receipt of detailed information on the study.

All ICFs must be available in the local and vernacular languages required at the study site and include subject information sheets/brochures that outline the study procedures. All ICF(s) must be signed and dated by the subject or a legally acceptable representative.

For subjects who are unable to read and write, the subject information sheet and ICF(s) should be read to the subject in his/her native language in the presence of an impartial witness who is literate and not affiliated with the study. The subject having understood the information given to him/her in the presence of an impartial witness will thumbprint the ICF(s) and the same will be countersigned by the impartial witness. If the subject or legally acceptable representative cannot read, then an impartial witness will witness and attest the entire consent process and will be required to sign the consent form. Confirmation of a subject's informed consent must also be documented in the subject's medical record prior to any testing under this protocol, including Screening tests and assessments.

The Investigator is responsible for ensuring that informed consent is obtained from each subject or legal representative and for obtaining the appropriate signatures and dates on the ICF prior to the performance of any protocol procedures and prior to the administration of study treatment. The Investigator will provide each subject with a copy of the signed and dated consent form while the originals will be retained in the Investigator's records.

